3.3 Study Endpoints

Safety Endpoints:

- AEs
- Stool Consistency Questionnaire indicative of a GI AE
- GI Signs and Symptoms Checklist indicative of a GI AE
- Clinical laboratory data
- ECG results
- FOBT results
- Vital signs
- Rate of urine output (24 hrs)

PK Endpoints:

AUC_t: Area under the plasma concentration-time curve from time 0 to the time (t) of last quantifiable concentration (C_t) calculated by the log-linear trapezoidal rule.

AUC_∞: Area under the plasma concentration-time curve from time 0 extrapolated to infinity. The terminal area from C_t to infinity was calculated by using the approximation as C_t/λ_z thus AUC_∞ = AUC_t + C_t/λ_z.

C_{max}: The maximum observed plasma concentration.

t_{max}: The observed time to reach maximum plasma concentration.

λ_z: The terminal-phase exponential rate constant as calculated from the negative slope of the regression line for the terminal linear portion of the LN transformed plasma concentration versus time curve.

$t_{1/2}$: The apparent terminal exponential half-life, calculated as $\ln(2)/\lambda_z$.

4 DEFINITION OF ANALYSIS SETS

For PK Assessments:

PK Analysis Set: The PK population will include subjects who received kindolor tosylate and had sufficient plasma concentrations to reliably calculate PK parameters.

For Safety Outcome Measures:

Safety Analysis Set: The safety population will include all subjects who received a dose of investigational product.

5 ASSESSMENT AND JUSTIFICATION OF STUDY ENDPOINTS

The Schedule of Assessments for the study is shown in **Table 1**.

5.1 Measurement of Plasma Concentrations of Kindolor and its metabolites and Determination of PK Parameters

Sample collection and analysis: Blood will be collected in 4 mL K₂EDTA Vacutainer tubes to obtain plasma for PK determination at the 29 times specified in the protocol timetable. The time of blood collection will be recorded. Blood samples will be placed on ice immediately after collection and then centrifuged to separate plasma within 30 minutes of collection.

Approximately 1 mL of plasma will be aliquoted into the primary vial and the remaining volume of plasma will be aliquoted into a back-up tube. The primary and back-up tubes are to be stored at -60°C to -80°C until analysis.

Plasma samples for DCUKA / 8-OH DCUKA determination will be analyzed using a validated LC/MS/MS method. A method validation report will be issued for the validated method and a bioanalytical report for the sample analysis.

PK analysis: The concentration-time profiles will be evaluated by non-compartmental analysis. Actual sample times will be utilized for calculations. Calculations of parameters will be performed with Phoenix WinNonLin 6.2 (Pharsight Corporation, St. Louis, MO). The **elimination rate constants (λ_z)** will be estimated from the terminal log-linear decline in plasma concentrations and $t_{1/2}$ **calculated as $\ln(2)/\lambda_z$** . Area under the plasma concentration curves will be determined till the last time of a quantifiable plasma concentration (AUC_t) by the log/linear trapezoidal rule and to infinity (AUC_∞) **based on the last plasma concentration (C_t) and λ_z** . The value of t_{max} will be the observed time of the highest plasma concentration and C_{max} would be the plasma concentration at that time.

Table 1 **Schedule of Visits and Assessments for Each Cohort**

| | Outpatient | Inpatient | | | | Outpatient | | Early Termination |
|--------------------------------------|------------|---------------|----------------|-----------|------------------|-------------|--------------------------------|-------------------|
| Activity | Screening | Clinic Intake | Treatment | Follow-up | Clinic Discharge | Follow-up | Telephone Contact ^a | |
| Study Day | -30 to -2 | -1 | 1 | 2 | 3 | 7±2 | | |
| Informed Consent | X | | | | | | | |
| Demographics | X | | | | | | | |
| Medical/Surgical History | X | update | | | | | | |
| Physical Examination | X | update | | | X | | | X |
| Height/Weight | X | Weight only | | | | Weight only | | Weight only |
| 12-Lead ECG ^a | X | | X | X | X | X | | X |
| Vital Signs ^b | X | X | X ^c | X | X | X | | X |
| Serum amylase | X | X | | | X | X | | X |
| Serum lipase | X | X | | | X | X | | X |
| Clinical Chemistry ^d | X | X | | | X | X | | X |
| Hematology ^e | X | X | | | X | X | | X |
| Coagulation ^f | X | X | | | X | X | | X |
| Urinalysis ^g | X | X | | | X | X | | X |
| Monitor urine output ^h | | | X | X | X | | | |
| Infectious Diseases ⁱ | X | | | | | | | |
| SARS-CoV-2 Antigen Test ^j | X | | | | | | | |

| | Outpatient | Inpatient | | | | Outpatient | | Early Termination |
|--|------------|---------------|-----------|-----------|------------------|------------|--------------------------------|-------------------|
| Activity | Screening | Clinic Intake | Treatment | Follow-up | Clinic Discharge | Follow-up | Telephone Contact ^a | |
| Study Day | -30 to -2 | -1 | 1 | 2 | 3 | 7±2 | | |
| Pregnancy Test ^k | X | X | | | | X | | X |
| Birth control methods | X | update | | | update | | update | |
| Sperm, ova, donation and breast feeding check | | X | | | | X | X | |
| FOBT | X | X | | | X | X | | |
| Urine Alcohol & Drug Screen ^l | X | X | | | | | | |
| Prior and Concomitant medications ^m | X | X | X | X | X | X | | X |
| Eligibility Checklist | X | Final check | | | | | | |
| Genetics Tests ⁿ | | X | | | | | | |
| Study Drug Administration | | | X | | | | | |
| Blood Samples for PK ^o | | | X | X | X | | | |
| Adverse Events ^p | | | X | X | X | X | | X |
| Stool Consistency | | X | X | X | X | X | | X |
| Final Subject Disposition | | | | | | X | | X |

^a A 12-lead resting ECG will be obtained at Screening, Day 1 prior to dosing, at 2, 6, 12, 24, and 48 hours post dose, and early termination.

^b Vital signs include sitting (3 minutes) blood pressure, and heart rate, and oral temperature, respiration rate, and pulse oximetry.

^c Blood pressure, and heart rate, respiration rate, and pulse oximetry will be taken pre-dose, then at 15, 30, 60 minutes and 2, 4, 6, 12, 24, and 48 hours post dose. Temperature will be taken pre-dose, 24, and 48 hours post dose. All vital signs will be taken at Day 3 before clinic discharge and Day 7.

- ^d Chemistry tests include albumin, alanine aminotransferase (ALT), aspartate aminotransferase (AST), blood urea nitrogen (BUN), creatinine, direct bilirubin, total bilirubin, alkaline phosphatase, creatinine phosphokinase (CPK), lactate dehydrogenase (LDH), sodium, potassium, chloride, calcium, inorganic phosphorus, bicarbonate, uric acid, total cholesterol, total protein, glucose, and triglycerides. Details are provided in Section 11.1.5.
- ^e Hematology tests include hematocrit, hemoglobin, red blood cell (RBC) count, white blood cell (WBC) count, absolute counts for neutrophils, lymphocytes, monocytes, basophils, eosinophils, and platelets.
- ^f Coagulation tests include prothrombin time (PT), activated partial thromboplastin time (aPTT), fibrinogen, and international normalized ratio (INR).
- ^g Urinalysis tests include specific gravity, pH, bilirubin, urobilinogen, ketones, protein, blood, glucose, nitrites, and leukocyte esterase. A microscopic evaluation will be performed if blood or leukocyte esterase are detected.
- ^h Urine output will be monitored by collection of urine for two 24 hr periods, starting with the morning void on Day 1 then again starting over with the morning void on Day 2 to 24 hours later.
- ⁱ Hepatitis A virus immunoglobulin M (HAV-IgM), hepatitis B surface antigen (HBsAg), hepatitis C virus antibody (HCV Ab), HIV antibodies (HIV Ab).
- ^j Results must be available within 72 hours of clinic intake.
- ^k A serum test for beta-human chorionic gonadotropin (β -hCG) will be performed on all women unless they are menopausal. For any post-menopausal females, a follicle stimulating hormone (FSH) test will be performed to confirm sterilization in lieu of a β -hCG test. If clinic intake is within 72 hours of a negative test, it does not need to be repeated at intake. At intake, a rapid test for β -hCG may be performed.
- ^l The urine drug test panel includes amphetamines, barbiturates, benzodiazepines, buprenorphine, cocaine, fentanyl, MDMA, methadone, methamphetamine, morphine, opioids, oxycodone, phencyclidine, and THC. Recent alcohol use will be assessed via ethyl glucuronide urine test strip.
- ^m Medication use in the two months prior to the start of screening and at any time during the study after signing informed consent will be recorded.
- ⁿ CYP2C9 polymorphisms
- ^o Blood for PK will be collected ~ 15 minutes prior to dosing, then at 0.25, 0.5, 1, 1.5, 2, 4, 8, 12, 24, and 48 hours after dosing.
- ^p GI AEs will be assessed specifically using a GI Signs and Symptoms Checklist, Stool Consistency Questionnaire, and endoscopy if indicated along with other laboratory tests as scheduled.
- ^q Telephone contact for males at 90 days and for females at 28 days after dosing.

5.2 Safety Endpoints

Adverse Events (AEs): An AE is defined as any reaction, side effect, or untoward event that occurs during the course of the clinical trial, whether or not the event is considered related to the investigational agent or clinically significant. For this study, AEs will include events reported by the subject, observed by clinical staff, clinically significant abnormal clinical laboratory results, or a positive pregnancy test. Reports of AEs will be elicited by a verbal probe (e.g., “How are you feeling?”) administered starting on Day 1 and daily during residency and at all other clinic visits.

Any events spontaneously reported by the subject or observed by the investigative staff will also be recorded. Each AE will be graded for severity, and the date and time of onset, cessation and resolution will be recorded.

Severity: All AEs (except application site reactions described below) will be graded according to the following definitions. Assignment of grade based on the intensity of symptoms and the degree of limitation of usual daily activities will be done according to severity using the following criteria:

- Grade 1:** Mild symptoms invoking a minimum degree of discomfort that are easily tolerated.
- Grade 2:** Moderate symptoms that result in a reduction in normal daily activity, but is not totally incapacitating. This may or may not require medical intervention.
- Grade 3:** Severe symptoms that may be totally incapacitating or result in marked reduction in normal daily activity. Medical intervention is usually required.
- Grade 4:** Potentially life-threatening event that requires emergency intervention or hospitalization.

Relationship: The degree of certainty for which the AE/SAE is attributed to the investigational product or alternative causes (e.g. natural history of the underlying disease, concomitant therapies, etc.) should be determined by how well the experience can be understood in terms of one or more of the following. The relatedness of an AE to the study drug is the best estimate of the causal relationship between the study drug and an AE at the time of reporting. Causality will be assessed by the Principal Investigator or designee.

The following drug relationships will be used for this clinical study:

Unrelated: There is no temporal relationship between the event and the administration of the study drug or the event is clearly due to the subject’s medical condition, other therapies, or accident.

Unlikely: There is evidence of exposure to the study drug but there is another more likely cause of the event.

Possibly Related: There is some temporal relationship between the event and the administration of the study drug and the event is unlikely to be explained by the subject's medical condition or other therapies.

Probably Related: The temporal relationship between the event and the administration of the study drug is compelling, and the subject's medical condition and other therapies cannot explain the event.

Definitely Related: The event follows a reasonable temporal sequence from administration of the medication or follows a known or suspected response pattern to the medication.

The categories of Definitely, Probably, and Possibly will be considered investigational product related with regards to summary statistics.

Serious Adverse Events. Each AE or reaction will be classified by the study investigator as serious or non-serious. The International Conference on Harmonization (ICH) Guideline for Industry: Clinical Safety Data Management: Definitions and Standards for Expedited Reporting, ICH-E2A March 1995, as implemented by the U.S. Food and Drug Administration defines SAE or reaction as any untoward medical occurrence that at any dose:

- results in death;
- is life-threatening; (*NOTE: The term "life-threatening" in the definition of "serious" refers to an event in which the subject was at risk of death at the time of the event; it does not refer to an event which hypothetically might have caused death if it were more severe.*)
- requires inpatient hospitalization or prolongation of existing hospitalization;
- results in persistent or significant disability/incapacity; or
- is a congenital anomaly/birth defect.

In addition, important medical events that may not result in death, be life-threatening, or require hospitalization may be considered a serious adverse drug reaction, when based on appropriate medical judgment that may jeopardize the subject and may require medical or surgical intervention to prevent one of the outcomes listed in the above definition.

Physical Examination.: A physical examination of the oral cavity, head, eyes, ears, nose, and throat, cardiovascular system, lungs, abdomen, extremities, skin, neuropsychiatric mental status and sensory/motor status, musculoskeletal system and general appearance will be performed during screening, weeks 4, 8, and 12.

Clinical Chemistry: ALT, Albumin, alkaline phosphatase, AST, bilirubin (total and direct), calcium, chloride, cholesterol, creatinine, GGT, glucose, phosphate, potassium, sodium, total protein, BUN, uric acid. Assessed at screening and weeks 4, 8 and 12.

Hematology: Hemoglobin, hematocrit, red blood cell count (RBC), reticulocytes, white blood cell count (WBC), platelets. Assessed at screening and weeks 4, 8 and 12

Urine drug tests: Urine drug tests will be used to assess candidates for recent use of amphetamines, barbiturates, benzodiazepines, cocaine, opiates, cannabinoids, phencyclidine, propoxyphene, and methadone. Assessed at screening and weeks 4, 8 and 12.

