#### 11.1.6. Reporting Pregnancy

Pregnancy in a study subject within 30 days after study drug administration must be reported to the investigator within 1 working day of becoming aware of the pregnancy. Subjects who become pregnant during the screening period prior to study drug administration will not be randomized to receive treatment.

If the subject becomes pregnant during the study or up 30 days after study drug administration, then a Pregnancy Reporting Form must be completed and emailed to Fast-Track within 24 hours of becoming aware of the pregnancy. Pregnancies must be followed to conclusions and an updated Pregnancy Reporting Form should be emailed to Fast-Track within 24 hours of becoming aware of the conclusion of the pregnancy.

Pregnancy in a study subject is not considered an AE. However, the medical outcome of an spontaneous abortion, stillbirth, or congenital anomaly is considered an SAE and must be reported to the sponsor within 24 hours of the site becoming aware of the event.

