#### 11.1.7. Classification of Adverse Event Intensity and Relationship to Investigational Product

The severity of AEs or SAEs will be in accordance with the FDA's "Toxicity Grading Scale for Healthy Adult and Adolescent Volunteers Enrolled in Preventive Vaccine Clinical Trials". For those not listed in the guidance, the following criteria will be used:

Mild:	An event that is usually transient, requiring no special treatment, and does not generally interfere with the subject's daily activities.
Moderate:	An event that interferes with usual activities of daily living, causing discomfort but poses no significant or permanent risk of harm to the subject. The event is usually ameliorated with additional specific therapeutic intervention.
Severe:	An event that interrupts usual activities of daily living or significantly affects clinical status. The event poses a significant risk of harm to the subject and hospitalization may be required, and typically requires intensive therapeutic intervention.

However, as gastric AEs are a potential concern, and the toxicity grading scale stated above, does not cover some of the more serious gastric AEs such as gastritis and gastric ulcer, the Common Toxicity Criteria for Adverse Events Grading Scale (version 5.0) will be used for the severity of these AEs.

The investigator must assess relationship to the investigational product based on the following criteria:

Unrelated:	The subject did not receive the investigational product, the temporal sequence of the AE/SAE onset relative to administration of the investigational product is not reasonable, or there is another obvious cause of the AE/SAE.
Unlikely:	There is evidence of exposure to the investigational product but there is another more likely cause of the AE/SAE.
Possible:	There is evidence of exposure to the investigational product, the temporal sequence of the AE/SAE onset relative to administration of the investigational product is reasonable, but the AE/SAE could have been due to another equally likely cause.
Probable:	There is evidence of exposure to the investigational product, the temporal sequence of the AE/SAE onset relative to administration of the investigational product is reasonable, and the AE/SAE is more likely explained by the investigational product than by any other cause.

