9.10 Handling of Missing Data

Adverse event data is not imputed. Missing dates are handled as follows:

- Missing day: The first day of the month will be used.
- Missing Month: The first month of the year will be used.
- Completely missing dates will remain missing, with no imputation applied. Consequently, time to onset and duration of such events will be missing.

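### The SAP's adverse-event rules conflict with the protocol on severity and causality, and its partial-date rule conflicts with the calendar, so some grades and relatedness calls are undefined and some imputed dates impossible

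*SAP*

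**What the plan says.** **Severity.** SAP 5.2: "All AEs (except application site reactions described below) will be graded according to the following definitions". The basis is "Assignment of grade based on the intensity of symptoms and the degree of limitation of usual daily activities". No application site reactions are described, and the product is an oral tablet. The same section counts clinically significant laboratory results as AEs. Protocol 11.1.7 applies the FDA toxicity grading scale first. Its own mild/moderate/severe definitions are a fallback: "For those not listed in the guidance, the following criteria will be used". Gastric AEs such as gastritis and ulcer go to the Common Toxicity Criteria v5.0. Protocol 11.3 grades laboratory AEs on the FDA scale.

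**Causality.** Under protocol 'Possible', timing is reasonable but "the AE/SAE could have been due to another equally likely cause". Under SAP 'Possibly Related', there is some temporal relationship and "the event is unlikely to be explained by the" subject's condition or other therapies. SAP 'Definitely Related' reads: "The event follows a reasonable temporal sequence from administration of the medication or follows a known or suspected response pattern to the medication". SAP 5.2 counts Possibly, Probably and Definitely as related in summaries.

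**Dates.** SAP 9.10: "Missing day: The first day of the month will be used". A missing month becomes January. Start and stop dates are not distinguished, and there is no lower bound at dosing.

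**Pregnancy.** SAP 5.2 lists a positive pregnancy test as an AE. Protocol 11.1.6 says: "Pregnancy in a study subject is not considered an AE". Protocol 11.1.8 nevertheless refers to an AE that is an ongoing pregnancy.

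**The concern.** SAP section 2 presents the SAP as describing and expanding on the protocol's analysis plan, so it has no stated basis for replacing protocol definitions. Safety and the MTD are the primary objective. Stopping criteria i to iii in protocol 8.13.2 depend on moderate and severe grades, including laboratory grades, and the MTD is defined by those criteria. After each cohort a statistician produces tables for the DSMB (protocol section 10, SAP 9.11). SAP Tables 5 and 7 to 13 are laid out by severity, and Tables 7 to 11 also by related or not related. If two definitions of grade and relatedness are in use, those tables need not match the grades on which escalation is decided. The date rule raises a separate problem: protocol 11.1.3 collects non-serious AEs only after dosing, so an onset imputed to before the dose is impossible.

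**Working it through.** **1. Severity, side by side.** SAP Grades 1, 2 and 3 are each worded as symptoms (mild, moderate, severe). Grade 4 is worded as a potentially life-threatening event. Take a laboratory value that the protocol's FDA scale would call Grade 2 or 3 in a subject who feels well. It meets the wording of none of SAP Grades 1 to 3, and meets Grade 4 only if life-threatening. The SAP therefore gives it no clear grade, while the protocol gives it one.

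**2. Causality, side by side.** Take an event with reasonable timing and an equally likely other cause, that cause being the subject's condition or another therapy.
- Protocol: 'Possible'.
- SAP 'Possibly': not met, because the other cause is not unlikely.
- SAP 'Unlikely': not met, because it needs a more likely other cause.
- SAP 'Definitely': can be met, because reasonable timing alone is enough.

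SAP 'Probably' asks for compelling timing and no other explanation, which is more than 'Definitely' asks. Protocol 'Definite' needs exposure, timing, the drug as the more likely cause and a known pattern, all together. The SAP scale is therefore not ordered, and it has a gap at the related/not-related boundary. The key to Listings 16 to 18 defines four codes (not related, unlikely, possibly, related), yet the shells print values 1 to 5.

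**3. Dates.** SAP 9.6 sets duration = stop − start + 1. Its two examples reproduce: same day gives 0 + 1 = 1, next day gives 1 + 1 = 2.

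*Inputs.* The documents give neither calendar dosing dates nor a missing-date rate. Assumptions: dosing is equally likely on each of 365 days, and onset is uniform over the first W days counted from the dosing day. W = 10 (0 to 9 days) matches a final visit 7 ± 2 days after dosing (protocol 8.8). Protocol section 5 places that visit after discharge instead, so a range of W is shown.

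*Onset day missing.* The imputed onset precedes dosing when dosing is not on the 1st and the onset falls in the dosing month. For an offset of j days, 12 dosing dates fail the first condition and 12j the second, leaving 365 − 12(1 + j). Summing over j = 0 to W − 1 and dividing by 365W gives

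share = 1 − 6(W + 1)/365.

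| W (days) | Share imputed to before dosing |
|---|---|
| 3 | 1 − 24/365 = 93.4% |
| 7 | 1 − 48/365 = 86.8% |
| 9 | 1 − 60/365 = 83.6% |
| 10 | 1 − 66/365 = 81.9% |
| 12 | 1 − 78/365 = 78.6% |

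A day-by-day enumeration agrees (2,990 of 3,650 for W = 10). The mean backward shift is about 14.7 days. With month and day both missing and W = 7, about 99% precede dosing.

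*Stop day missing.* Let onset be on the dosing day and the true stop 0 to 7 days later. If the stop is in the dosing month, duration = 1 − (day of month) + 1, which is ≤ 0 whenever dosing is on the 2nd or later. The same formula with W = 8 gives 1 − 54/365 = 85.2% (2,488 of 2,920).

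*Example.* Dosing 20 March, AE 22 to 23 March, true duration 2 days.
- Start day missing: onset 1 March, 19 days before dosing, duration 23 − 1 + 1 = 23 days.
- Stop day missing: duration 1 − 22 + 1 = −20 days.
- Start month missing: onset 22 January, 57 days before dosing in a non-leap year, duration 61 days.

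**The case against.** The other side has a good case on consequences, and much of it stands.

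- A reader might infer that the SAP caps a severe laboratory value at mild. It does not: Grade 1 also requires symptoms, and Grade 4 is not worded by symptoms. The defect is the absence of a clear grade.
- A reader might infer that events drop out of 'related'. This is not shown. An equally likely cause also fails SAP 'Unlikely', and a well-timed event can meet SAP 'Definitely', which counts as related. SAP 'Possibly' names only the subject's condition and other therapies as rival causes, and these are healthy volunteers excluded for regular medication. The split is ambiguous, with no demonstrated direction.
- A reader might infer that stopping decisions will be wrong. The stopping rule, laboratory grading and investigator assessment all sit in the protocol, and the Medical Monitor advises on whether criteria are met. The SAP misleads only if its definitions are used for grading or for DSMB tables.
- A reader might apply the 82% and 85% to all AEs. They apply only to AEs with a missing day. These should be few: subjects are confined from Day -1 to Day 3, onset and cessation times are recorded, and monitors review the source records.
- A reader might infer that misdated events leave the AE tables. The SAP defines no treatment-emergent window, so frequencies are unaffected.
- On pregnancy, the protocol is not consistent with itself, so the SAP is not simply at odds with a clear rule.

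These points limit the harm. They do not reconcile the definitions or make the imputed dates possible.

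**Conclusion.** The point holds as a conflict of definitions plus a faulty date rule, and the SAP text needs correcting before it is used for outputs. Severity matters most, because the same word or grade can mean different things in the SAP tables and in the protocol's stopping criteria. That conclusion needs no numerical assumption. The causality wording leaves the related/not-related split ambiguous, again by definition alone.

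The date rule matters less. Given a missing onset day, 79% to 93% of imputed onsets precede dosing over windows of 12 down to 3 days. Given a missing stop day, about 85% of durations are zero or negative under the stated onset and duration assumptions. The damage is confined to listed study day, time to onset and duration. The overall number of affected events cannot be stated, because no missing-date rate is given.

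**What to change.** 1. **Severity and causality.** First reconcile protocol 11.1.7 with Appendix B: Appendix B puts GI checklist AEs on the FDA scale, while 11.1.7 puts gastric AEs on the Common Toxicity Criteria v5.0. No view is taken here on which is right. Then align SAP 5.2 with the reconciled 11.1.7 and delete the application-site exception.
2. **Listings 16 to 18.** Use the five relationship categories in the key.
3. **Pregnancy.** Reconcile SAP 5.2 with protocol 11.1.6 and 11.1.8 on whether pregnancy is an AE.
4. **Partial start dates.** Use the later of the dosing date and the first day of the known period. SAEs are collected from consent, so apply the dosing-date floor to an SAE only when it is known to be post-dose; otherwise use the consent date as the floor.
5. **Partial stop dates.** Use the earlier of the last day of the known period and the last contact, never before the start.

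In the March example with the start day missing, the onset becomes 20 March and the duration 23 − 20 + 1 = 4 days. That is still an approximation to the true 2 days, but a possible value; the floor takes the pre-dose share for post-dose AEs to 0%. The whole-day duration rule in SAP 9.6 can stay.

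Cost: SAP wording and listing keys, plus short protocol clarifications for items 1 and 3. No new data or subjects are needed.
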